### **Technical Setup**

- Motion-Tracking Devices: A designated space with sufficient room (2–3 meters clear space) for Kinect-based tracking.
- Secure Storage: Each site must have secure cabinets or a locked office for paper records (e.g., consent forms).

## Ethical and Governance Approvals

- Each hospital may require local governance or R&D approval in addition to overarching ethical approval (e.g., IRAS).
- Formal site agreements must be in place to ensure compliance with data protection (GDPR) and institutional policies.

## Staff Training

- Staff at both sites will receive a brief orientation on ReHabGame's operation, the motion-tracking sensors, and participant safety protocols.
- Any site-specific health and safety training required by hospital policy (e.g., manual handling, infection control) must be completed by the research team.

1. Identification & Recruitment
  - At each site, clinical teams (physiotherapists, occupational therapists, rehab consultants) will introduce the study to eligible patients and, if they express interest, refer them to the research team for formal screening.
  - Potential participants will receive an information sheet and have an opportunity to ask questions before providing written informed consent.
2. Baseline Assessments
  - Participants will undergo baseline clinical evaluations (e.g., Fugl-Meyer Assessment), and relevant questionnaires.
  - These may take place in a private clinic room or dedicated rehabilitation space.
3. ReHabGame Intervention
  - Participants will use ReHabGame in designated therapy areas equipped with the Kinect hardware.
  - Session frequency and duration will follow the study protocol (e.g., 1–2 sessions per week over 6–8 weeks).
  - Research staff or designated clinical staff will supervise sessions, ensuring correct usage and participant safety.
4. Data Collection
  - Quantitative: System logs (range of motion, frequency of play), standardized clinical scales (pre-/post-intervention).
  - Qualitative: Questionnaire to gather feedback on user experience and feasibility.
5. Follow-Up Assessments
  - Post-intervention evaluations will be conducted to assess changes in upper-limb function and gather final feedback.
  - Data will be entered into secure, password-protected electronic databases, ensuring confidentiality and compliance with data protection laws.

## Resource Optimization

- Leveraging the expertise and facilities at sites ensures sufficient staff support, therapy spaces, and participant pool, thereby strengthening the study's feasibility and overall quality.

## 7 SAMPLE AND RECRUITMENT

This pilot RCT will recruit 92 participants (46 per cohort), allowing for ~20% attrition to achieve at least 90 completers in total. Recruitment will take place over 12 months across two sites (neurorehabilitation and orthopaedic physio clinics).

- **Recruitment sources:**
  - Referrals from participating physiotherapists and neurologists
  - Clinic screening of outpatient caseloads
  - Posters and leaflets in waiting areas
  - Direct approach **via the treating clinician** during routine appointments; research staff contact patients only **after clinician referral and consent to be contacted**.

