## STUDY SUMMARY

It may be useful to include a brief synopsis of the study for quick reference. Complete information and, if required, add additional rows.

Study Title	ReHabGame: A Markerless, Game-Based Rehabilitation program
Internal ref. no. (or short title)	ReHabGame

Study Design	
Parallel, two-cohort (Neurological, MSK), two-arm RCT
 
Arms (within each cohort):
 
 
1. Usual Care only
 
2. Combined ReHabGame + Usual Care
 

Study Participants	
 
• Age 18+ years
 
• Ability to follow simple instructions and give consent
 
• No severe cognitive impairment (MoCA <math>\geq 22</math>)
 
• Stable medical condition (no recent cardiovascular event)
 

Planned Size of Sample (if applicable)	
Planned Sample Size per cohort (Neurological or MSK):
 
23 participants per arm: 2 arms = 46 participants
 
Total across both cohorts:
 
46 (Neurological) + 46 (MSK) = 92 participants
 
Allowing for ~20% attrition,

Follow up duration (if applicable)	4-week post-intervention follow-up (Week 12)
Planned Study Period	
Participants to be randomised to:
 
 
1. ReHabGame: 30–45 min sessions, 2x/week for 6–8 weeks
 
2. Usual care: standard physio sessions, 2x/week for 6–8 weeks
 

Research Question/Aim(s)	
Primary Objectives: feasibility endpoints
 
(Combined = ReHabGame + usual care; Control = usual care only)
 
 
• Neurological cohort:
 

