## 5 STUDY DESIGN and METHODS of DATA COLLECTION AND DATA ANALYSIS

Type: Parallel, two-cohort (Neurological vs MSK), two-arm randomized controlled trial

- Arms (within each cohort):
  1. Usual-care physiotherapy only
  2. Combined ReHabGame + usual-care

Allocation: 1:1 randomisation, stratified by baseline severity (high vs low) within each cohort

- Blinding:
  - Outcome assessors blinded to group assignment

- Participants & therapists unblinded (interventions are overt)
- Duration: 6–8 weeks of intervention (2 sessions/week) + 4-week follow-up
- Sample size: 23 per arm per cohort (46 per cohort; 92 total), allowing ≈20% attrition.

Domain	Instrument & Timing
Demographics & History	Structured questionnaire at Week 0 (age, sex, diagnosis, time since onset/surgery, comorbidities)
Primary Outcomes	- Neurological: Fugl–Meyer Assessment (upper extremity) at Weeks 0, 8- MSK: SPADI at Weeks 0, 8
Secondary Outcomes	- Neurological: Barthel Index at Weeks 0, 8- MSK: DASH, pain VAS, goniometric ROM at Weeks 0, 8
Interim Metrics	At Week 4 for all: SUS, engagement survey, adverse-event checklist, quick FMA-UE subset (neuro) or SPADI re-test (MSK), Kinect snapshot metrics
Follow-up Metrics	At Week 12: SUS, engagement survey, adverse-event update, optional brief functional check
Motion-Tracking Data	Automatically logged each session via Kinect: range of motion, smoothness (jerk), repetition count, completion time, accuracy
Session Adherence	PDF session log (date, duration, pain VAS, issues) maintained by participant; automatically generated session report PDFs summarising movement metrics
Qualitative Feedback	Semi-structured interview or written feedback at end of Week 8 (usability, barriers, facilitators, motivation)
Safety Monitoring	Adverse events recorded at every session and via AE checklist at Weeks 4, 8, 12; severity and relatedness noted

All analyses conducted separately within each cohort on an intention-to-treat basis,  $\alpha = 0.05$  two-sided.

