## **7.2 Sampling**

To ensure adequate feasibility data and allow for up to 20% attrition, we will recruit 108 participants in total (Kunselman, 2024).

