### **7.2.1 Size of sample**

Allocated as follows:

- o Per cohort: 46 participants
- o Per arm (1:1): 23 participants
- o Expected completers per arm:  $\geq 18$  participants
- o Total completers:  $\geq 72$  participants

This sample size is not powered for definitive hypothesis testing but is sufficient to:

1. Estimate recruitment, retention, and adherence rates with acceptable precision.
2. Generate variance estimates for the primary outcomes (FMA-UE in the Neurological cohort; SPADI in the MSK cohort) to inform sample-size calculations for a future definitive trial.

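### Protocol section 7 gives two recruitment totals (92 and 108) and two completer totals (90 and 72); at 20% attrition only 92 recruited with about 72 to 74 completers is consistent

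*Protocol*

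**What the plan says.** The protocol states the sample size in five places.

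- **Study Summary:** 23 per arm, 46 per cohort, 92 across both cohorts, followed by the words "Allowing for ~20% attrition", where the sentence stops in the text available.
- **Section 5 (Study design):** "23 per arm per cohort (46 per cohort; 92 total), allowing ≈20% attrition".
- **Section 7 (Sample and recruitment):** the trial "will recruit 92 participants (46 per cohort), allowing for ~20% attrition to achieve at least 90 completers in total".
- **Section 7.2 (Sampling):** to "allow for up to 20% attrition, we will recruit 108 participants in total".
- **Section 7.2.1 (Size of sample):** directly after the 108, an allocation of 46 per cohort and 23 per arm. The item "Expected completers per arm" is at least 18, and total completers are at least 72.

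The total also matters elsewhere. Under Planned Statistical Analyses (Interim Analyses), an independent Data Monitoring Committee reviews safety after half of the participants have completed Week 8. The Safety Review item in section 5 repeats this as a midpoint at about 50%.

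**The concern.** Section 7 contradicts itself in one sentence, because the completer count cannot follow from the recruitment number and the attrition allowance given beside it. Section 7.2 then gives a recruitment total that its own subsection does not allocate.

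Two things are at stake. First, the trial has no single recruitment total against which a feasibility study can judge whether it recruited as planned, and no single expected completer count against which to judge retention. Second, the safety review is triggered by a percentage of participants, so its timing depends on which total is meant.

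**Working it through.** **Inputs.** Recruited N: 92 (Study Summary, sections 5 and 7; also the sum of the allocation in 7.2.1) or 108 (section 7.2). Completers C: at least 90 (section 7) or at least 72 (section 7.2.1). Attrition d: about 20% (Study Summary, sections 5 and 7) or up to 20% (section 7.2).

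**Formulas.** Expected completers = N × (1 − d). Recruits needed = C / (1 − d). Implied attrition = 1 − C / N.

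**Step 1: the figure in section 7.** 92 × 0.8 = 73.6, so the stated 90 is not reproduced. The implied attrition is 1 − 90/92 = 2.2%.

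**Step 2: the figures in section 7.2.1.** 23 × 0.8 = 18.4 per arm, stated as at least 18. Four arms (two in each of two cohorts) give 4 × 18 = 72. Both figures are reproduced. The allocation adds up to 4 × 23 = 2 × 46 = 92, not 108.

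**Step 3: all four pairings at 20% attrition.**

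| Recruited N | Completers C | Implied attrition | N × 0.8 | C / 0.8 | Consistent? |
|---|---|---|---|---|---|
| 92 | 90 | 2.2% | 73.6 | 112.5, so 113 | No |
| 92 | 72 | 21.7% | 73.6 | 90 | Yes, apart from rounding down per arm |
| 108 | 90 | 16.7% | 86.4 | 112.5, so 113 | No |
| 108 | 72 | 33.3% | 86.4 | 90 | No |

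**Step 4: size of the discrepancies.**

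- Completers in section 7: 90/73.6 = 1.22 and 90/72 = 1.25, an overstatement of about 22% to 25%.
- Recruitment: 108 − 92 = 16 participants, and 108/92 = 1.17, a difference of 17%.
- Safety review trigger: 0.5 × 92 = 46 or 0.5 × 108 = 54 participants.

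**The case against.** The strongest defence is that the design itself is settled. Every place that gives a cohort target says 46. Section 6 assigns the MSK cohort to one site and the neurological cohort to the other, so each site finds one number to recruit to. On this view 108 and 90 are two stray figures, each appearing once, in a pilot that section 7.2.1 says is not powered for definitive testing. This stands: the ambiguity lies in the trial total and what depends on it, not in the cohort or arm sizes, and no power claim fails.

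It can also be said that the completer counts are floors, so at least 90 and at least 72 do not exclude each other. As inequalities that is true, but it does not rescue section 7, since 90 cannot be reached from 92 at 20% attrition.

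A reader might infer more than the documents support:

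- **That the precision claim rests on 90 completers.** It does not. The statement about acceptable precision and variance estimates is in section 7.2.1, beside the 72.
- **That the denominators of the feasibility rates are affected.** They are not. The Descriptive / Feasibility Metrics section defines the rates from observed counts (screened, eligible, randomised, completing Week 8), not from the planned total.
- **That 108 came from inflating 90 by 1.2 instead of dividing by 0.8.** The product does equal 108, but so does 6 × 18. The protocol shows no derivation and never pairs 108 with 90. Only the mismatch can be asserted.
- **That the Study Summary means 92 after attrition, so that 92/0.8 = 115 would be recruited.** The sentence is cut off, possibly when the PDF was read, and sections 5 and 7 both present 92 as already including the allowance.

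Finally, section 7.2 attaches its sample-size reference to the 108, so it cannot be assumed without asking that 92 is the intended number. This point also stands and shapes the fix.

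**Conclusion.** The contradiction is real and is in the current text. Section 7 claims at least 90 completers where its own figures yield about 72 to 74, and section 7.2 states 108 recruited where its own allocation adds up to 92. The set of 92 recruited and 72 completers is the only one that agrees with 20% attrition and with the per-arm and per-cohort figures throughout, which makes 108 and 90 the outliers.

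The practical effect is an ambiguous recruitment total (92 or 108), an ambiguous safety review trigger (46 or 54 participants) and an overstated completer count in section 7. It should be corrected because these are basic figures that the trial is run against.

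This rests on two assumptions: attrition is a flat 20% in every arm, as the protocol implies, and the 50% in the safety trigger refers to the planned number of participants.

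**What to change.** The sponsor should confirm one recruitment total and bring sections 7 and 7.2 into line with the Study Summary, section 5 and section 7.2.1.

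If 92 is confirmed:

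- in section 7.2, replace 108 with 92;
- in section 7, replace the 90 completers with at least 72 completers (18 per arm).

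The safety review trigger is then 46 participants without further change. The cost is wording, plus a stated number of completers that looks less favourable; no participants are added.

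If the sponsor intended 108, or at least 90 completers, the change is more than wording. A total of 108 means 108/4 = 27 per arm and about 86 completers, and 90 completers at 20% attrition need 113 recruits. In either case the cohort and arm sizes in the Study Summary and in sections 5, 7 and 7.2.1 would have to be restated.

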### Screening process:

- Interested patients receive an information sheet and undergo preliminary eligibility check (by phone or in person).
- Eligible patients invited for a face-to-face screening visit to confirm criteria, obtain written informed consent, and complete baseline assessments.
- **Retention strategies:**
  - Flexible session scheduling (morning/afternoon slots)
  - Interim "progress report" PDFs after each session to maintain engagement

### 7.1.1 Common Inclusion Criteria

1. Age 18+ years
2. Able to understand study information and provide written informed consent
3. MoCA  $\geq 22$  (no severe cognitive impairment)
4. Medically stable (no major cardiovascular event or surgery within past 3 months)

### 7.1.2 Cohort-Specific Inclusion Criteria

- **Neurological cohort:**
  1. Clinically diagnosed stroke, traumatic brain injury, or relapsing-remitting multiple sclerosis
  2. Upper-limb motor impairment: FMA-UE score 20–50 at baseline
  3.  $\geq 3$  months post-stroke or  $\geq 6$  weeks post-MS relapse
- **MSK cohort:**
  1. Diagnosed rotator cuff repair ( $\geq 6$  weeks post-op), adhesive capsulitis, or shoulder arthroplasty (< 6 months)
  2. Pain  $\leq 6/10$  on resting VAS
  3. Active shoulder elevation  $\geq 30^\circ$
  4. On a stable physiotherapy regimen ( $\leq 2$  sessions/week)

### **7.1.3 Exclusion Criteria (both cohorts)**

1. Uncontrolled hypertension or significant cardiac arrhythmia
2. Severe spasticity (Modified Ashworth  $\geq 3$ ) or gross joint instability
3. Severe visual or hearing impairment preventing safe game use

Participants meeting all common and relevant cohort-specific inclusion criteria, and none of the exclusion criteria, will be enrolled and randomized.

## **7.2 Sampling**

To ensure adequate feasibility data and allow for up to 20% attrition, we will recruit 108 participants in total (Kunselman, 2024).

### **7.2.1 Size of sample**

Allocated as follows:

- o Per cohort: 46 participants
- o Per arm (1:1): 23 participants
- o Expected completers per arm:  $\geq 18$  participants
- o Total completers:  $\geq 72$  participants

This sample size is not powered for definitive hypothesis testing but is sufficient to:

1. Estimate recruitment, retention, and adherence rates with acceptable precision.
2. Generate variance estimates for the primary outcomes (FMA-UE in the Neurological cohort; SPADI in the MSK cohort) to inform sample-size calculations for a future definitive trial.

### **7.2.2 Sampling technique**

Participants will be recruited using a consecutive convenience sampling approach within each cohort at the two collaborating clinical sites:

2. Identification of potential participants:
  - o Treating therapists screen their outpatient caseloads and post-surgical lists for patients meeting broad eligibility (age, diagnosis category).
3. Invitation and screening:
  - o All eligible patients are approached in person or by telephone, provided with study information, and invited to a formal screening visit.
  - o Those who consent and meet detailed inclusion/exclusion criteria at screening are enrolled.
4. Randomisation:

- Enrolled participants are then randomised 1:1 within their cohort (Neurological vs MSK) into the two trial arms using a stratified block randomisation scheme, with stratification by baseline severity (high vs low) to ensure balance across arms.

This approach ensures that we capture a representative sample of the clinic's neurorehabilitation and MSK shoulder populations while maintaining rigorous allocation to the intervention arms.

### 7.3 Recruitment

**Aim:** To describe how eligible participants—including those for both intervention and control groups—are identified, approached, and enrolled in the study, ensuring a transparent and ethical process from initial contact to informed consent.

#### 7.3.1 Sample identification

##### 1. Clinical Gatekeepers—Identification of Potential Participants

Treating clinicians—including physiotherapists, occupational therapists, and rehabilitation consultants—at the research centers or/and hospitals will serve as clinical gatekeepers. Their role will include:

- Identifying potential participants based on the study's inclusion and exclusion criteria.
- Screening for both the intervention group (Rehabgame users) and control group (usual care recipients).
- Ensuring that only those patients deemed medically and cognitively suitable to participate are referred.
- Avoiding any form of coercion by relying on existing therapeutic relationships to introduce the study in an ethical and respectful manner.

##### 2. Referral to the Research Team Once a suitable participant is identified:

- The clinician will briefly introduce the study's purpose, confirming preliminary interest without going into extensive detail.
- If the individual expresses interest, the clinician will refer them to the research team, either:
  - By sharing the research team information with them or sharing their contact details securely with the research team (in accordance with GDPR/local data protection guidelines); or
  - By facilitating a direct introduction to the research team (e.g., during an outpatient visit or ward round).
- Referrals will include candidates for both study arms, ensuring equitable identification.

##### 3. Initial Contact by the Research Team

A designated member of the research team—not involved in the patient's direct clinical care—will conduct the next steps:

- Make initial contact via phone, video call, or in person at a convenient time.
- Provide the Participant Information Sheet (PIS) and offer a comprehensive explanation of the study aims, procedures, and randomisation (if applicable).
- Answer any immediate questions and allow participants time to consider their involvement.

### 7.3.2 Consent

**Aim:** To outline the procedure for obtaining **informed, voluntary, in-person consent** from participants before any study-related activities commence, in accordance with ethical, legal, and Good Clinical Practice (GCP) standards.

This section also clarifies the **non-consenting role of QR code scanning**, which is used solely for session-level attendance confirmation.

#### Initial Discussion

- Only individuals with legitimate clinical access to medical records and clinic schedule lists will review these prior to obtaining consent. This access is limited to members of the patient's usual care team (e.g., treating physiotherapists, rehabilitation consultants, or clinical supervisors) who are already authorised to view these records as part of their professional duties. The purpose of this review is solely to identify potentially eligible participants in accordance with the inclusion and exclusion criteria.
- Research staff or research assistants will not have access to identifiable patient records or clinic schedules prior to consent. Their involvement will commence only after a patient has been identified by the treating clinician, has been approached about the study by that clinician, and has provided informed consent to be contacted by the research team.
- This discussion will cover:
  - The purpose and objectives of the study
  - Study procedures and duration
  - Potential risks and benefits
  - Data handling, confidentiality, and withdrawal rights
- Participants are actively encouraged to ask questions throughout.

#### Provision of Written Materials

Each participant (or representative) will receive the **Participant Information Sheet (PIS)** and the **Consent Form**, written in plain language and approved by the Research Ethics Committee (REC).

Participants will be given a minimum of **24 hours** to review the documents, consult others if desired, and consider their decision without pressure.

#### Opportunity to Ask Questions

Before signing the consent form, participants will have the opportunity to clarify any part of the study and confirm understanding with the research team.

## Assessment of Capacity

Capacity will be assessed by the **clinical gatekeeper** prior to referral, and again confirmed by the research team before obtaining consent.

Capacity assessment ensures the participant can:

- Understand the research and its implications
- Retain the information long enough to make an informed decision
- Weigh up choices and communicate a voluntary decision

## Protecting Vulnerable Participants

- In a rehabilitation setting, some participants may be more vulnerable to perceived coercion.
- To minimize this risk:
  - Consent will be obtained in a private setting, away from direct clinical staff
  - Participants will be reminded that participation is voluntary, and their usual care will not be affected by their decision
  - They may withdraw from the study at any time, without giving a reason

## Signing the Consent Form

When all questions have been answered and the participant confirms understanding:

- The participant and the researcher will sign and date the consent form
- A copy is provided to the participant, and the original is stored securely in the study documentation

## Use of QR Code – Session-Level Confirmation Only

- This QR code may be scanned at each session to:
  - Confirm attendance
  - Log session data (e.g., time, session type)
- Important: QR code scanning is used solely to confirm attendance and link session-level quantitative data to the participant's study ID; it does not replace informed consent.
- Ongoing verbal confirmation of willingness to proceed with each session will be encouraged.

## 8 ETHICAL AND REGULATORY CONSIDERATIONS

**Aim:** To explain how the study's aims and methods comply with ethical principles and relevant regulatory frameworks, highlighting participant risk-benefit balance, data protection measures, and adherence to legal requirements.

